Alternative Treatment to Standard Treatment of Adolescent Suicidality: Telehealth services encompass an emerging intervention due to the need for social distancing measures. They encompass crisis interventions that include safety planning, therapeutic interventions and emergency medication consultations. Telehealth services will not be the same at all sites, but involve similar services.

At CCHMC, our study team developed the term Outpatient Crisis Intervention Clinic (OCIC) to encompass the programs from the 4 individual sites, CCHMC, Northwell Health, Nationwide Children's and Children's Health, that provide similar, but not the same, services. The 4 programs that encompass the term OCIC have some variation in treatment approaches and duration, however all 4 programs have crisis intervention work in common, including appointments that occur soon after emergency department visits for crisis intervention. In comparison to inpatient psychiatry, Outpatient Crisis Intervention Clinic (OCIC) provides more intensive therapeutic services for adolescent suicidality with frequent family focused mental health appointments, specific therapeutic interventions for suicidality while outside of the hospital, and more thorough safety planning to prevent future suicidal events. OCIC has advantages because it provides a more intensive level of short-term (about two to six weeks) support with multiple therapeutic visits for adolescents with suicidality and their families each week starting within three days of the crises. OCIC provides these services for the adolescents and their families who are waiting for outpatient services without exposing these adolescents to the above-mentioned disadvantages

Gaps in Knowledge about Outcomes of Alternative Treatment of Adolescent Suicidality: Few programs have been developed that bridge the vulnerable period of time spanning between Emergency Room evaluation for adolescent suicidality to outpatient care,⁸⁸⁻⁹⁰ and even fewer that provide intensive treatment in an outpatient setting for teens.¹⁷ As such, there is tremendous need to develop and test optimal treatment strategies for adolescents during this high risk period, as highlighted in Objective 8.4 of the National Strategy for Suicide Prevention, to “promote continuity of care and the safety and well-being of all patients treated for suicide risk in emergency departments or hospital inpatient units.”⁹¹

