5.7. Screen Failures

Screen failures are defined as participants who consent to participate in the clinical study but are not subsequently included in the study. A minimal set of screen failure information is required to ensure transparent reporting of screen failure participants to meet the Consolidated Standards of Reporting Trials (CONSORT) publishing requirements and to respond to queries from regulatory authorities. Minimal information includes demography, screen failure details, eligibility criteria, and any serious adverse events (SAE).

Individuals who do not meet the criteria for participation in this study (screen failure) may be rescreened. Rescreened participants will be assigned the same participant number as for the initial screening.

6. Treatments

Study treatment is defined as psychiatric treatment within either Outpatient Crisis Intervention Clinic (OCIC), on an Inpatient unit, or telehealth crisis intervention services. Participants will be placed in the treatment setting by the assessing clinician. These therapeutic interventions are available whether or not the subject agrees to participate in the study.

Telehealth crisis intervention services (telehealth CIS) is defined as psychiatric services provided via telehealth services that is expected to be scheduled within 7 business days of the crisis assessment. Interventions can be with a social worker, therapist or psychiatrist. Services are not in person and occur over a computer video/phone system.

Inpatient treatment includes supportive individual therapy, improving patient's coping skills, family meetings about safety planning, and medication management.^{6-9, 81}

OCIC services include crisis psychotherapy/intervention, evidence-based screening/risk assessments, coordination of care/referral to an ongoing provider, short-term therapy/crisis treatment, safety planning, and/or referral and linkage to follow-up care. Treatment in OCIC may include group therapy, individual therapy, and/or family therapy, depending on the site. Please

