see below for full description of services by site. Adolescents in OCIC will be referred to a psychiatrist for medication management as needed. OCIC provides crisis intervention therapy and/or components of Cognitive Behavior (CBT), Dialectical Behavior Therapy (DBT), mindfulness CBT, Relapse Prevention CBT, and/or Supportive Psychotherapy. The length of time in OCIC and telehealth CIS can range from around one to six weeks depending on the needs of the patients and families. Due to the pragmatic approach to the research design, interventions provided will be site specific but all sites will include the crisis intervention component, including crisis stabilization (therapeutic intervention) and safety planning and assessment. Additionally, patients will have the expectation of being scheduled to be seen within 7 business days of the ED visit for follow up care. The charts below outline a description of the OCIC program, Inpatient services, and Telehealth CIS services provided at each of the four sites.⁴⁰⁴³ The following is an explanation of services provided in the treatment arms. All treatment is clinically based and data will be collected. No decisions on treatment will be part of this study and the data from this study will not be shared with clinicians to alter care.

Site	Describe intervention with patient	Describe intervention with family	Length of visit	Length of treatment	Staff performing treatment	Plan if subject has increased risk of suicide
Cincinnati	
A crisis intervention appointment will entail:
 
 1. Identification of current crisis and precipitants 2. Exploration of feelings/emotions using components of CBT, DBT and other therapies 3. Identification and exploration of coping skills and resources 4. Safety planning and assessment 	
1. Family support 2. Safety assessment and planning 3. Referral to psychiatric provider for evaluation for need of medication 4. Referral and connection to outpatient provider for continued care.
	60 min or longer as needed	Average 1-3 sessions, longer as needed	Licensed Independent Social workers, Clinical Counselors, APRNs and child and adolescent psychiatrist for medication management	Pt would be referred to the ED for evaluation or admitted to inpatient by clinical staff.

Site	Describe intervention with patient	Describe intervention with family	Length of visit	Length of treatment	Staff performing treatment	Plan if subject has increased risk of suicide

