6.2. Treatment Compliance

For this study, treatment compliance is defined as adhering to appointments assigned by assessing clinician to telehealth or OCIC and not leaving against medical advice (AMA) if assigned to inpatient treatment. For patients who are not treatment compliant, attempts will be

made by the study staff to follow up and encourage recommended treatment. Study staff will work with PIRC or equivalent to complete up to two phone calls or text messages to attempt to contact patients who do not show for scheduled telehealth appointments, OCIC appointments, or inpatient recommendation. If we are unable to contact these patients or they refuse any or all follow up treatment (including telehealth, OCIC, inpatient or outpatient recommendations), we will continue to follow them until they withdraw from the study. If patients refuse telehealth, OCIC or inpatient treatment from the emergency department or crisis assessment, we will continue to follow these patients until they withdraw from the study. For patients who are AMA from the inpatient unit, this process of following up regarding services will be addressed by the inpatient treatment team. It is standard of care for inpatient treatment teams to not provide prescriptions and follow up services for AMA's but this practice varies based on the inpatient treatment team. If the AMA (from inpatient treatment) patient remains in our study, we will encourage the AMA patient to return to treatment (inpatient, OCIC, and/or telehealth outpatient).

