8.2.1. Time Period and Frequency for Collecting AE and SAE Information

All AE and SAE will be collected from the start of treatment until 180 day follow-up or when the participant completes milestones.

For serious adverse events that result in injury, disability, death or significant functional impairment, each site is required to notify the DSMB and the IRB within 24-48 hours of the knowledge of the occurrence one of these SAE's, how the site personnel became aware of it, and

the response. The DSMB will make a determination as to whether the risks and benefits of the study are altered by the event.

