During the baseline ED visit or assessment, all patients and families who receive telehealth or OCIC will receive safety planning, lethal means restriction education, emergency contact numbers, and will be advised that if a situation of potential harm should arise that they should go to the nearest ED by their assessing clinician. During the period between ED discharge and their first appointment in telehealth or OCIC, based on clinical judgment of the research team, patients and their families may be contacted by a research team member to further discuss safety planning, provide lethal means restriction education, provide emergency contact numbers, and/or advise that if a situation should arise that they should go to the nearest ED. Families will also be directed that they can contact research staff (during business hours) if they have any of the above stated needs and research staff can provide referrals. If patients in the inpatient arm of the study show signs they are clinically worsening, the patient will remain on the inpatient unit and hospital protocol will be used to determine the most appropriate safety measures. If the patient showed signs of worsening in the telehealth or OCIC arm of the study or while in the outpatient setting, the patient will be admitted into inpatient psychiatry, will attend partial hospitalization and/or will be evaluated in the ED. All decision on treatment and care will be decided by the patient's treating clinician. Study staff will follow and document outcomes.

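### AE/SAE collection opens at treatment start, so it leaves out enrolled time before a first telehealth or OCIC visit and never opens for participants who do not start treatment

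*Combined protocol and SAP*

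**What the plan says.** The collection window in section 8.2.1 reads: "All AE and SAE will be collected from the start of treatment until 180 day follow-up or when the participant completes milestones". No other section gives a different opening date, or any date for a participant who never begins treatment.

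Section 6 (Treatments) fixes what treatment means: "Study treatment is defined as psychiatric treatment within either Outpatient Crisis Intervention Clinic (OCIC), on an Inpatient unit, or telehealth crisis intervention services". Telehealth CIS is "expected to be scheduled within 7 business days of the crisis assessment". The general text of the same section gives the expectation of "being scheduled to be seen within 7 business days of the ED visit for follow up care". The background (section 2.2) has OCIC visits "each week starting within three days of the crises".

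Section 6.2 does not drop people who decline treatment: "If patients refuse telehealth, OCIC or inpatient treatment from the emergency department or crisis assessment, we will continue to follow these patients". Their follow-up ends only at withdrawal, and the same applies to participants who miss their appointments and cannot be reached. Under SA4 in section 3, the no-show group is expected to have earlier and more suicidal events than the other participants.

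Section 8.2.2, on detecting AEs and SAEs, recognises the wait as a period of its own ("During the period between ED discharge and their first appointment in telehealth or OCIC") and makes research contact within it optional: "based on clinical judgment of the research team, patients and their families may be contacted by a research team member". It also plans a coordinator contact 24 to 48 business hours after the baseline assessment, whichever setting was assigned.

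**The concern.** A safety window should cover everyone the study follows, for as long as it follows them. Here the opening is tied to an event that comes later for outpatients and, for some participants, does not come at all.

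Section 8.2 counts accidental injury and death arising from other risk behaviors as AEs or SAEs, alongside suicidal ideation and attempts. It also plans to set the proportion of suicidal AEs observed in the study against the rate expected from the literature. If a site applies the window as written, an injury before a first telehealth visit, or at any time in a no-show, is not collected as an AE. The observed proportion could also omit suicidal events from the group that SA4 expects to do worst. Whether a given event reaches the DSMB would then depend on how the site reads section 8.2.1.

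**Working it through.** The plan states no figure on this point, so there is none to reproduce. The check is a cross-reading plus a conversion of days.

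**1. When treatment starts.** By the section 6 definition it starts with care in the assigned setting. For telehealth and OCIC that is the first visit. The ED or crisis assessment is not part of it.

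**2. Longest wait before a first outpatient visit.** The inputs are 7 business days (section 6) and, for OCIC, three days (section 2.2). Counting from the day after the crisis and ignoring holidays, 7 business days is:

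| Day of crisis | Calendar days |
|---|---|
| Sunday to Wednesday | 9 |
| Saturday | 10 |
| Thursday or Friday | 11 |

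Share of follow-up = wait ÷ length of follow-up:

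| Wait | Of 90 days | Of 180 days |
|---|---|---|
| 3 days | 3/90 = 3.3% | 3/180 = 1.7% |
| 9 days | 9/90 = 10.0% | 9/180 = 5.0% |
| 11 days | 11/90 = 12.2% | 11/180 = 6.1% |

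These are ceilings for visits kept to schedule. The scheduling text sets an upper limit, and the clock runs from the crisis, whereas only time after consent is enrolled time. Sections 5.1 and 6.1 recruit once a setting has been assigned, so a participant can be enrolled but untreated. Section 4.1 dates baseline within 72 hours of admission to the setting, so the enrolled part of the wait may be shorter.

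**3. Participants who never start.** With no treatment start, the window covers 0 of 180 days, however long or short the usual wait is. This applies to enrolled no-shows and refusers. Inpatients who leave against medical advice have started treatment, so their window does open.

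**4. Section 8.2.1 against section 8.2.2.** The detection methods begin before the first visit, with the coordinator contact and the optional contacts during the wait. The collection window begins at the visit. The two sections therefore disagree about whether an event learned of in between is to be collected.

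**5. Other capture routes.** The Suicidal Event Form is completed at baseline and every two weeks (sections 8 and 8.1), and the EHR is searched weekly for suicidal events (section 4.1). Neither depends on treatment start. Both target suicidal events, and neither sets a window for other AEs and SAEs.

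**6. Number of events affected.** This would need the event rate between crisis and first visit, the timing of consent, and the number of no-shows and refusers. The documents give none of the three.

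**The case against.** The strongest reply is that the protocol captures far more than one sentence of section 8.2.1 suggests. Section 8.2 makes suicidal ideation and attempts AEs reportable to the DSMB. The outcome form and EHR search reach no-shows, because section 6.2 keeps them in follow-up. Section 8.2.4 calls for weekly reports on suicidality and adverse events for each participant, and for reporting of all unexpected AEs and SAEs. Section 8.2.2 shows that early detection was intended. All of this stands, and it confines the point to AE/SAE collection and reporting. It does not remove the point, because these provisions give no opening date for non-suicidal injuries and other SAEs before or without treatment.

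Four stronger readings are tempting, and the documents do not support them.

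- *A sizeable share of events is lost.* Section 2.2 puts almost half of six-month reattempts in one month. Spreading that half evenly over 30 days gives 0.5 × 9/30 = 15% to 0.5 × 11/30 = 18% in the wait. But that month follows discharge from OCIC, so it comes after treatment, and the figure covers reattempts only.
- *The outpatient arms will look safer than inpatient.* The comparison in section 8.2 is of the study with the literature, not of arm with arm. Nor do the documents say that inpatients start at once; the background describes bed shortages and boarding.
- *A death before a first visit escapes the 24-48 hour notice.* Section 8.2.1 ties that notice to the site's knowledge of the event and does not mention treatment start.
- *The primary analysis loses events.* Step 5 of the working shows otherwise.

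**Conclusion.** The point holds in a limited form. As written, the AE/SAE window leaves out enrolled time before a first telehealth or OCIC visit and never opens for enrolled participants who do not start treatment. It is also inconsistent with sections 6.2 and 8.2.2. For participants seen on schedule, the omitted time is at most 5.0% to 6.1% of 180 days, or 1.7% on the three-day figure for OCIC. For those who never start treatment, all of it is omitted. What is at stake is the completeness of AE/SAE records and DSMB/IRB reporting, mainly for non-suicidal injuries and other SAEs, and the comparison of observed with expected suicidal AEs.

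This rests on a literal reading of section 8.2.1 with the section 6 definition, and on some participants being enrolled before or without a first visit, which sections 5.1, 6.1 and 6.2 allow. No event count should be attached to it.

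**What to change.** In section 8.2.1, replace the words that open the window at treatment start with: *from enrolment (consent), for every enrolled participant, whether or not treatment starts*. State that the index event is not counted as a new AE or SAE. In the DSMB AE/SAE listings, identify participants who never started treatment, so that their events can be seen and the comparison with expected rates has a clear denominator.

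Collection need not reach back before consent, and this point gives no reason to alter the end of the window. The change affects no clinical care. It costs one amended sentence, a short rule for the index event, a flag in the DSMB listings, and a few more AE/SAE reports.

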8.2.2. Method of Detecting AE and SAE

Clinical worsening of suicidal ideation/behavior is assessed similarly at each site. On the inpatient units at each site, clinical worsening of suicidal ideation/behavior is assessed daily with observation and by interviewing the patient. For patients in the OCICs and telehealth outpatient clinics at every site, clinical worsening of suicidal ideation/behavior is assessed by the treating clinician during each visit or if the parent/legal guardian calls to discuss the patient. The Dallas OCIC uses a clinical approach and assessment tools to evaluate worsening of suicidal ideation/behavior while the other sites use a clinical approach (with collateral information and interviews of the patient). Furthermore, clinical worsening of suicidal ideation/behavior will be assessed through the use of surveys and questionnaires that patients and/or guardians will fill out about every 2 weeks.

The risk of lack of improvement or worsening of psychiatric illness will be addressed by monitoring subjects closely during assessments.

For this proposed research, we will plan to have the research coordinator at each site contact the legal guardians and patients by phone (or in person) within 24-48 business hours of the baseline assessment to review the referral to either inpatient psychiatric treatment, telehealth, or OCIC treatment and to review safety planning and identify any concerns or needs for referral. At Nationwide Children's Hospital (NCH), they also plan to have text message outreach to patients within the 48 hours after discharge. Text messaging may also be considered as a potential method within 48 hours of discharge at other sites if phone calls are not successful in reaching the legal guardians and patients.

During the baseline ED visit or assessment, all patients and families who receive telehealth or OCIC will receive safety planning, lethal means restriction education, emergency contact numbers, and will be advised that if a situation of potential harm should arise that they should go to the nearest ED by their assessing clinician. During the period between ED discharge and their first appointment in telehealth or OCIC, based on clinical judgment of the research team, patients and their families may be contacted by a research team member to further discuss safety planning, provide lethal means restriction education, provide emergency contact numbers, and/or advise that if a situation should arise that they should go to the nearest ED. Families will also be directed that they can contact research staff (during business hours) if they have any of the above stated needs and research staff can provide referrals. If patients in the inpatient arm of the study show signs they are clinically worsening, the patient will remain on the inpatient unit and hospital protocol will be used to determine the most appropriate safety measures. If the patient showed signs of worsening in the telehealth or OCIC arm of the study or while in the outpatient setting, the patient will be admitted into inpatient psychiatry, will attend partial hospitalization and/or will be evaluated in the ED. All decision on treatment and care will be decided by the patient's treating clinician. Study staff will follow and document outcomes.

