2.2. Background

Suicide is a leading cause of death for adolescents in the United States.¹⁻⁵ Adolescent suicidality includes suicidal thoughts, intent, plans, and attempts.⁷³ Suicidality does not include nonsuicidal self-injury (NSSI) because it does not include intent to die.⁷⁴ The primary outcome measure for this proposed research will be the time to first recurrence of a suicidal event.⁷⁵ A suicidal event is defined as: a suicide attempt, interrupted attempt, hospitalization because of suicidal risk, an emergency/urgent evaluation because of suicidal risk, and a death by suicide. NSSI is not our primary target and we will focus on adolescents who present with suicidal thoughts and suicide attempts which can also include NSSI. Therefore, to improve generalizability, we will collect data on NSSI even though it is not part of our primary outcome.

Our stakeholder partner, [name], Executive Director, NAMI of Southwest Ohio, clarified that the most acceptable terminology is death by suicide or died by suicide rather than committed or completed suicide.⁷⁶ For adolescents in the United States in 2015, suicide was the third leading cause of death between the ages of 10 and 14, and the second leading between the ages of 15 and 34.^{2, 4, 5} For girls (ages 15 to 19), the suicide rate doubled from 2007 to 2015 and was at its highest peak in 40 years in 2015 with a rate of 5.1 per 100,000. For males (ages 15 to 19), the suicide rate increased by 31% between 2007 and 2015 when the rate was 14.2 per 100,000.³ The Youth Risk Behavior Surveillance Survey estimated that of high school students, 16% reported seriously considering suicide, 13% reported creating a plan to kill themselves, and 8% reported trying to kill themselves in the previous 12 months.⁷⁷ Adolescent suicidal behavior is common, with more than 1 million attempts and 4,600 deaths by suicide each year.⁵² There is a clear need for development of treatment programs both aimed at preventing adolescent suicide attempts, as well as addressing recurrent suicidal ideation and promotion of safety following an attempt.^{78, 79}

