Scores on the CHRT were also significantly reduced by discharge with propensity scores (26.01 ± 10.43 vs. 16.72 ± 10.03 ; $p < .0001$) as well as active suicidal ideation scores (4.85 ± 3.63 vs. 1.91 ± 2.40 ; $p < .0001$) showing a marked improvement compared to baseline. Preliminary clinical outcomes at discharge from [name]'s OCIC and at six month follow-up were positive. Patients were improved at the time of discharge on self-report of depressive symptoms

and suicidal ideation and behavior. 286 of the 364 adolescents (or 78.57%) responded to the 6 month follow up questions. In total, 8.7% and 27.3% of the 286 respondents reported a suicide attempt and event, respectively, within 6 months of discharge from OCIC. Reattempt rates at 6 months were at 8.7%, with almost half these occurring within one month after discharge. Suicidal events (includes attempts, emergency room visits or hospitalization) at 6 months were at 27.3%. It is possible that the suicidal events were higher than attempts because the adolescents were following their safety plan and reaching out for professional support when suicidal ideation increases. Patients who made an attempt within the 6 month follow up period had a history of more previous attempts, higher self-report of depressive symptoms at discharge, and higher levels of active suicidal ideation (CHRT) at entry and exit.

Those patients who had a suicide event at follow-up were more likely to be female, had more previous attempts, and had higher self-reported and parent reported depression at entry in the program. Those with a suicidal event also had higher self-reported active suicidal ideation at entry into the program.

Due to the fact that telehealth CIS is only currently being widely used for mental health services in this population group, CHRT-SR and other follow up data is not currently known. This research will seek to fill in this gap of knowledge.

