6.3. Treatment After the End of the Study

Follow up care after the end of this study will be decided by the participants' parents'/guardians', therapist, mental health professional, and/or physician.

7. Discontinuation Criteria

It is unlikely that a patient will be discontinued from the study during the inpatient, telehealth, or OCIC phase of the study. If patient experiences worsening symptoms while inpatient, this treatment will be extended to meet their needs as identified by inpatient clinicians. Patient in the OCIC or telehealth treatment arms with worsening symptoms may be recommended for evaluation in the ED, referral for inpatient, and/or connected to outpatient services as identified by a qualified mental health clinician. If a patient is involved in an adverse event that is associated with study procedures, leading to harm, the DSMB and external medical monitor may identify the need for removal from the study for safety concerns. This is unlikely but will be monitored by the DSMB, EMM and IRB

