9.2.1. Efficacy Analyses

Endpoint	Statistical Analysis Methods
Primary	The primary outcome measure for this proposed research will be the time to first recurrence of a suicidal event. We will examine if the treatment option can predict the “time to the first suicidal event” using the Cox-proportional hazard model.
Secondary	The secondary outcome is Satisfaction with Life (SL), which will be measured every two weeks. The treatment effect on such time-series

	data will then be analyzed using mixed-effect ordinary logistic regression model.
Exploratory	Will be described in the statistical analysis plan finalized before database lock

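### The primary composite can score worsening during the index stay differently in the inpatient arm, and no planned analysis separates suicidal behaviour from use of care

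*Combined protocol and SAP*

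**What the plan says.** Section 2.2 defines the primary event as "a suicide attempt, interrupted attempt, hospitalization because of suicidal risk, an emergency/urgent evaluation because of suicidal risk, and a death by suicide". Two of the five components, hospitalization and emergency evaluation, are use of care.

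The response to worsening depends on the setting. For a patient in telehealth, OCIC or the outpatient setting, Section 8.2.2 says "the patient will be admitted into inpatient psychiatry, will attend partial hospitalization and/or will be evaluated in the ED". For a worsening inpatient it says "the patient will remain on the inpatient unit and hospital protocol will be used to determine the most appropriate safety measures". Section 7 agrees on the inpatient side: "If patient experiences worsening symptoms while inpatient, this treatment will be extended to meet their needs as identified by inpatient clinicians". On the outpatient side Section 7 is softer: ED evaluation or inpatient referral may be recommended, and connection to outpatient services is another option.

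On analysis, Section 9.2.1 states "The primary outcome measure for this proposed research will be the time to first recurrence of a suicidal event" and gives a Cox model for it. Section 9.2.2 refers safety back to the same outcome. Section 9.2.3 sets a 3-month horizon for the Aim 1 Cox model. Section 9.2 calls itself a summary and defers the full analysis plan to a later document. Time zero for the Cox model is not stated.

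**The concern.** A clinical deterioration in the first days can be an event in the telehealth or OCIC arm and not in the inpatient arm, where the response is to stay longer. Section 3 hypothesizes that telehealth carries more risk than inpatient care, and the scoring difference pushes that comparison the same way.

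There is also a question of interpretation that affects every arm comparison, telehealth versus OCIC included. Commenting on its pilot data, Section 2.2 says: "It is possible that the suicidal events were higher than attempts because the adolescents were following their safety plan". An excess of composite events could therefore mean more suicidal behaviour or more help-seeking. The documents contain no between-arm analysis that would tell these apart.

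**Working it through.** **Inputs from the documents**
- OCIC pilot, 6 months after discharge, 286 respondents: 27.3% with an event and 8.7% with an attempt, attempts being included among events (Section 2.2).
- Index inpatient stay L: 6 to 8 days, depending on site (Section 6).
- Horizons T: 6 months of follow-up (Section 4.1), taken as 180 days, and 3 months for Aim 1 (Section 9.2.3), taken as 90 days.
- Expected completers: telehealth 75, OCIC 75, inpatient 70, total 220 (Section 9.1).

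**Assumptions not in the documents**
- True risk is equal in all arms, and the clock starts with index treatment in every arm.
- The hazard during the first L days is f times the later hazard, with f from 1 to 6.
- The pilot composition applies throughout. Events that are care use only cannot be counted during the inpatient stay, but all are counted in the outpatient arms.

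**1. The plan's own figure.** The plan gives no figure for this issue. Its one figure for the primary comparison is power of 0.70 (Section 9.1). From the stated inputs, events = 70 × 0.19 + 75 × 0.10 = 20.8, and at HR 2.8 with two-sided 0.05 the Schoenfeld formula gives 0.65. The R function used is not named, and nothing below depends on this figure. Its inputs are still telling: the inpatient 19% is a readmission rate and the OCIC 10% is an attempt rate.

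**2. Composition of the composite.** Patients with an event: 0.273 × 286 = 78. With an attempt: 0.087 × 286 = 25. With an event but no attempt: 53 of 78, or 1 − 8.7/27.3 = 68%.

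**3. Size of the scoring effect.** The inpatient arm keeps only 8.7/27.3 = 0.319 of its hazard during the stay. The ratio of cumulative hazards, outpatient to inpatient, is

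[(T − L) + fL] / [(T − L) + 0.319 fL]

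For example, with f = 6, L = 8 and T = 180: (172 + 48)/(172 + 15.3) = 220/187.3 = 1.17.

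| f | L (days) | 180 days | 90 days |
|---|---|---|---|
| 1 | 6 | 1.02 | 1.05 |
| 1 | 8 | 1.03 | 1.06 |
| 3 | 6 | 1.07 | 1.14 |
| 3 | 8 | 1.09 | 1.18 |
| 6 | 6 | 1.13 | 1.26 |
| 6 | 8 | 1.17 | 1.34 |

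**4. Could this alone give a significant result?** Take the worst row, 75 versus 70 patients, with a 6-month outpatient risk of 27.3%.
- Expected events over 180 days: 75 × 0.273 + 70 × 0.238 = 37. Over 90 days: 75 × 0.172 + 70 × 0.132 = 22.
- The Schoenfeld chance of two-sided significance is about 8% and 10%, against a nominal 5%.

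**5. A less favourable assumption.** Suppose a share w of every arm worsens at some point in index treatment, only the outpatient response counts, and later risk is b. The ratio is ln[(1 − w)(1 − b)] / ln(1 − b). For w from 2% to 10% it runs from 1.06 to 1.33 at b = 27.3%, and from 1.19 to 2.00 at b = 10%. The documents give no value for w.

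**6. What a behaviour-only analysis can carry.** At pilot rates, 220 patients give 0.273 × 220 = 60 with a composite event and 0.087 × 220 = 19 with an attempt over 6 months. Two arms (145 patients) give 12.6 attempts. At HR 2.8, power is 0.40 (Freedman-type formula) to 0.45 (Schoenfeld).

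**The case against.** The strongest reply is that the asymmetry is narrow. After discharge, inpatient-arm patients are in the outpatient setting and are scored as everyone else is. An attempt on the unit still counts. The mechanism does not touch telehealth versus OCIC. Worsening outpatients do not always generate an event: Section 7 allows connection to outpatient services, the Section 2.2 definition does not name partial hospitalization, and Section 8.2.2 leaves treatment decisions to the treating clinician. If the clock starts after index treatment, the mechanism disappears, though start times then differ between arms. All of this stands, and it limits the claim.

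A reader might infer that the endpoint's structure alone could confirm the telehealth hypothesis. The documents do not support that. Step 4 puts the chance of a significant result only slightly above nominal, and the larger ratios in step 5 need a share worsening that the documents do not give. Section 9.1 also plans for a higher rate in the inpatient arm, and there the same effect would dilute a difference.

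The 68% has limits too. It comes from one OCIC program, after discharge, with no inpatient comparator. It shows what the composite contains and does not measure bias between arms. Some patients without an attempt may have had an interrupted attempt, which the pilot summary does not list separately.

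Finally, the plan is not blind to suicidality apart from care use. CHRT-SR ideation is collected every two weeks and drives the interim rule, C-SSRS data are collected, and the deferred analysis plan could add more. But ideation is not behaviour, no between-arm analysis of attempts is specified, and the AE review in Section 8.2 compares with literature rates, not between arms.

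**Conclusion.** The point holds in a limited form. Scoring can differ by arm mainly during the index stay (6 to 8 days, longer if extended) and only in comparisons with the inpatient arm. It leans toward telehealth appearing riskier than inpatient care, with an illustrative apparent hazard ratio of 1.02 to 1.17 over 180 days and 1.05 to 1.34 over 90 days. This rests on equal true risk, a clock starting with index treatment, the pilot composition, and an early hazard 1 to 6 times the later one.

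The interpretive gap is broader. If about two-thirds of patients with an event have no attempt, the composite alone cannot show whether any arm difference reflects suicidal behaviour or care use.

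It would be tempting to conclude that a difference carried by ED or hospital use should not be reported as harm. That does not follow. With power of 0.40 to 0.45 even at HR 2.8, the absence of a difference in attempts would say little. The gap is worth closing before database lock, and the primary endpoint need not change.

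**What to change.** Keep the composite as the primary endpoint. In Section 9.2.1:

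1. Define time zero and the handling of the index stay, the same way in all arms.
2. Pre-specify a supportive between-arm Cox model for time to first attempt, interrupted attempt or suicide death.
3. Pre-specify a table of first events by component and arm, and interpret the composite alongside both. State that the supportive model will not be used to dismiss a composite difference.
4. Confirm that the Suicidal Event Form records the component and its date; its fields are not shown in the documents.

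Separately, reconcile the accounts in Sections 7 and 8.2.2 of the outpatient response to worsening with each other and with the event definition in Section 2.2, including whether partial hospitalization counts as an event.

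The cost is some definitions, one model and one table, with no new data collection if the form holds what is needed. The drawback is precision: about 19 attempts in 220 patients over 6 months, and fewer by 3 months, mean a wide interval.
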